5.1 Study Design

- Describe experimental design of the study. Include sequential and/or parallel phases of the study, including durations, and delineate which interventions are standard of care and which are research.
- Include a description of how anticipated risk will be minimized and include an analysis of risk vs. potential benefit.
- Provide description of the study population (delineate all categories of subjects – patients, providers, family members, employees, etc.). Include anticipated enrollment numbers
- Include rationale for including or excluding certain populations – in particular vulnerable populations.
- As applicable, provide information on any added protections for vulnerable populations.

The setting will be primary care and diabetes specialty clinics at the two facilities. This will be a naturalistic intention-to-treat study in which all patients in these clinics are eligible to consent to participate and data from all arms will be included in the analysis regardless of whether the patient listens to the audio. Also, there will be no exclusion criteria. We have no preconceptions about who could benefit: for instance, counter-intuitively, a severely hearing impaired patient who has difficulty following face-to-face encounters might benefit if they choose to share the audio with a caregiver.

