Aim 1: Assess the impact of an open access audio program on two behaviors (patient activation, treatment plan adherence), two services (ED utilization, inpatient admissions), and two chronic condition measures (glycosylated hemoglobin, blood pressure).

Aim 1 hypotheses will be tested by comparing patients randomized to arms 1 (intervention) and 2 (control) on the outcomes specified in figure 2. Following an informed consent process (see "Informed Consent Procedures" p 20, below), the Veteran will carry an audio into the encounter, regardless of the arm to which they are assigned. They'll return the recorder when they leave. In Arm 1, the Veteran and provider will each be given access to a passcode to a website that will stream the audio from any internet enabled device. Audio is streamed rather than downloaded, to prevent inadvertent sharing. Also, with streaming, the platform can track for the research team whether, when, the number of times, and how long the audio is listened to by either party. In Arm 2 neither the Veteran nor provider will have access to the audio, but the research team can listen to it.

The decision to give the provider access to the audio whenever the patient has access is based on conversations with providers during the proposal planning process who have said they would not feel comfortable having a patient listen to a visit that they couldn't also listen to if they wished to do so. In Open Access Notes, both providers and patients have access to documentation of the visits, and so it seems logical that Open Access Audio should work in parallel, particularly given that current technology makes this feasible. The research team will be able to track whether and when either party access the audio. This will not contaminate isolating the impact of the audio on the patient (e.g. were the provider to call the patient after

listening to the audio to correct an error or elaborate), since we'll know when providers log in, enabling us to control for it as a co-variate or exclude if it's a rare event.

Aim 2: Assess the impact of open access audio on provider communication behavior and on their attention to patient contextual factors (i.e. individual Veterans' needs and circumstances relevant to planning effective care).

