(C) Upon arrival, they will complete the informed consent process and the brief literacy screen (REALM-SF), receive the audio recording device, and instructions based on the arm of the study to which they are randomized, as to whether to keep the audio recording out in the open (Arms 1 and 2), or to conceal it (Arm 3). A code, assigned to the encounter, will be utilized as the ID on the literacy screen, and linked to the patient name and medical record number stored in the cross walk file on a separate VHA approved server. After the encounter, patient and provider participants will receive a link to access the audio if they were in Arm 1. If they are called prior to completing the process, their appointment takes precedence and they will not participate.

(D) In addition to pre-visit outreach, the RA will recruit patients at an information desk on site when they arrive in the waiting area with a poster and a brochure inviting Veterans to learn more if they are interested.* This will occur until recruitment targets are met. Those who are seeing a participating provider and want to participate will complete the informed consent process and the brief literacy screen (REALM-SF). They will receive a \$20 gift card to remunerate them for the additional work of completing the survey after the visit and for randomly participating in a follow up call for the PAM survey. If the Veteran is called prior to completing the process, their appointment takes precedence and they will not participate.

***COVID-19 MODIFICATION: As long as infection transmission remains a risk the following protocol modification will be in place:**

- Only phone based recruitment will occur.
- The informed consent process will be completed over the phone prior to the visit, except for the final signing process.
- The RA will still meet the patient in the waiting area, both masked. However, it will be a very brief meeting and they will remain 6 feet apart. There will be a small fold

up table in the waiting area. The patient will sign the consent form, collecting the audio recorder, and complete the 7 item REALM-SF which consists of reading out loud 7 words, and takes less than 1 minute.

- Post visit, the patient will return the audio recorder to the table and collect \$20 gift card from the research assistant. Again, the RA will maintain a physical distance of at least 6 feet and will remain masked.

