As summarized in Table 4, we will apply several measures to assess the effectiveness of the intervention, testing hypotheses to achieve Aims 1 and 2. For each hypothesis, comparisons between arms will be made using mixed-effect linear or logistic regression as appropriate for the outcome, with a fixed effect of study arm, VA site, and primary vs. secondary care setting, and a random effect of provider to accommodate clustering of visits within providers. Of primary interest is the direction, magnitude, and significance of the regression coefficient associated with study arm. Primary analysis will compare arms on an intention-to-treat basis, without regard to whether audio made available in Arm 1 is actually accessed by anyone; secondary analyses will include covariates representing whether, how often, and by whom (patient or provider) audio is actually accessed in Arm 1 to assess the impact of audio use (vs. availability). As patients will be randomized to arms, we do not expect demographic or other patient differences among arms, but will conduct tests for differences, and if any variables differ significantly among arms, we will include them as covariates in the regression models.

Table 4. Hypotheses and evaluation strategy for effectiveness of intervention (Aims 1 and 2)

Hypothesis	Evaluation Strategy
1A: OAA increases patient activation.	Administer PAM (Appendix A-1) 1-2 weeks post visit via phone call and compare scores in Arm 1 vs. Arm 2
1B: OAA increases care plan adherence, including fewer no-shows and more on-time refills.	Utilizing the data warehouse measure Return Visit Adherence (RVA) and refill rates (PDC) ^{24,32,33} in Arms 1 vs. 2.
1C: OAA reduces Hgb A1c and BP	Same as above: Utilizing data warehouse measure A1c and BP.
2A: Providers obtain higher scores on measures of communication behavior when they know they are being recorded.	Completed by trained RA off of Audio: SEGUE checklist for communication completed by research team (Appendix A-2) ²⁵ , comparing randomly sampled visits in Arm 2 vs Arm 3.
2B: Providers obtain higher scores on measures of attention to patient contextual factors essential to care planning when they know they are being recorded.	4C for contextualization of care ³⁴ , comparing randomly sampled visits in Arm 2 vs Arm 3.

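### Audio access happens after randomization and only in Arm 1, so neither adjusting for it nor excluding provider log-ins isolates the effect of use; the primary intention-to-treat comparison is sound

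*Combined protocol and SAP*

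**What the plan says.** All references are to the combined protocol and SAP.

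- **Primary rule.** Section 5.1 (Study Design) states that "data from all arms will be included in the analysis regardless of whether the patient listens to the audio". Section 5.6 (Data Analysis) makes the primary analysis intention-to-treat, "without regard to whether audio made available in Arm 1 is actually accessed by anyone".
- **When and where access occurs.** Section 5.2: "After the encounter, patient and provider participants will receive a link to access the audio if they were in Arm 1". Section 5.1, Aim 1: "In Arm 2 neither the Veteran nor provider will have access to the audio".
- **Provider log-ins.** Section 5.1, Aim 1, considers a provider who listens and then contacts the patient. It says: "This will not contaminate isolating the impact of the audio on the patient". The reason given is that log-ins are recorded, "enabling us to control for it as a co-variate or exclude if" they are rare. Rare is not defined, and the sentence does not say which analysis it means.
- **Access covariates.** Section 5.6: "secondary analyses will include covariates representing whether, how often, and by whom (patient or provider) audio is actually accessed in Arm 1". The stated purpose is to learn about use as distinct from availability.
- **Access data in general.** Section 5.1 (Audio recording technology) says the HealthPAL usage data will enter the Aim 1 analysis but gives them no role.

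**The concern.** Arm is assigned before the visit. Logging in is a later choice by the patient or provider, and it is zero by design in Arm 2. Patients who log in may differ from those who do not in technology literacy, engagement or health. Arm 2 contains the same mix of people, but nobody there can be identified as a would-be accessor. A model containing access therefore compares self-selected groups.

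At stake is the secondary answer on use versus availability. As planned, it mixes any effect of listening with the characteristics of those who listen. The provider sentence has the same fault. A log-in may be prompted by what happened in the visit, and adjusting for it or dropping those patients has no counterpart in Arm 2.

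**Working it through.** The plan gives no figure on this point to reproduce, so the check is algebra followed by an illustration on the PAM.

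**Inputs**
- PAM SD 19.5 and 924 patients (Section 5.6), taken as 462 per arm.
- Planned PAM difference: 60.0 − 56.0 = 4 points (Table 4.1).
- Access share q in Arm 1: 72%, the average listening rate in the review cited in Section 2.0; also 40%, assumed.
- D: the accessor minus non-accessor difference that would exist with no audio effect, after covariates. **Assumed**; its size and sign are unknown.
- Two-sided 5% tests, clustering ignored.

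**Two-arm model with arm and access terms.** Because access is zero throughout Arm 2:
- arm coefficient = mean(Arm 1 non-accessors) − mean(Arm 2)
- access coefficient = mean(Arm 1 accessors) − mean(Arm 1 non-accessors)

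Suppose there is no audio effect and non-accessors average m. Accessors then average m + D. By randomization Arm 2 averages m + qD. The arm coefficient is m − (m + qD) = −qD, and the access coefficient is D. Both should be zero. Fitted within Arm 1 only, the arm term disappears but the access coefficient is still D.

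**Standard errors**
- SE(ITT) = 19.5 × √(2/462) = 1.283
- SE(access) = 19.5 × √(1/(462q) + 1/(462(1−q))) = 2.021 at 72% and 1.852 at 40%

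| q | D | Arm bias −qD | Access bias | Null access effect called significant |
|---|---|---|---|---|
| 72% | 1 | −0.7 | +1 | 8% |
| 72% | 2 | −1.4 | +2 | 17% |
| 72% | 4 | −2.9 | +4 | 51% |
| 40% | 1 | −0.4 | +1 | 8% |
| 40% | 2 | −0.8 | +2 | 19% |
| 40% | 4 | −1.6 | +4 | 58% |

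Negative D reverses the signs. In 2,000 simulated trials with no audio effect, 72% access and D = 4, the access coefficient averaged +3.9 (significant in 51%) and the arm coefficient −2.9. Across the null scenarios simulated, the comparison with no access term stayed within 0.04 points of zero and rejected in 4.5% to 5.3% of runs.

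**Provider log-ins.** If a share r of Arm 1 is excluded and differs by D from those kept, the Arm 1 mean shifts by −rD. In a linear model without other covariates, an Arm 1-only log-in indicator has exactly the same effect on the arm coefficient, since it also leaves Arm 1 non-log-ins against all of Arm 2. With |D| = 4:
- r = 5%: 0.05 × 4 = 0.2 points, false-positive rate 5.3%
- r = 10%: 0.10 × 4 = 0.4 points, false-positive rate 6.1%

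With |D| = 6 the shifts are 0.3 and 0.6 points and the false-positive rate is at most 7.4%.

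**The alternative for an effect of use.** A complier average causal effect (CACE) divides the intention-to-treat difference by q. The 95% half-widths are:
- intention-to-treat: 1.96 × 1.283 = 2.5 points
- CACE at 72%: 2.515/0.72 = 3.5 points
- CACE at 40%: 2.515/0.40 = 6.3 points

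A direct effect d of assignment that bypasses listening biases the CACE by d/q. One point becomes 1.4 at 72% and 2.5 at 40%. The CACE is less biased than the access coefficient only if |d| < q|D|. For |D| = 2 that means below 1.4 points at 72% or 0.8 at 40%.

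**The case against.** **The primary analysis is already protected.** A reader might infer that Aim 1's main result will be contaminated. The documents do not support that. Section 5.6 ignores access by anyone, which includes providers, and puts access covariates in secondary analyses. The usage-data sentence under Audio recording technology fits that slot; it is ambiguous rather than contradictory. This stands in full.

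**The exclusion need not breach intention-to-treat.** A reader might infer a flat contradiction. But the log-in sentence names no analysis, and an exclusion confined to a secondary analysis contradicts nothing in Section 5.6. It breaks the rule only if applied to the primary comparison, and truly rare exclusions move the estimate little. This also stands. What does not survive is the claim that the log-in step leaves the patient effect uncontaminated.

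**Planned adjustment may deal with selection.** Section 5.6 adjusts for age, gender, race and literacy, and obtains internet access for the intervention arm. These plausibly predict log-in, but they remove only the selection they measure. The model's "a random effect of provider to accommodate clustering of visits within providers" handles correlation among visits, not which patients choose to listen.

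**CACE is not clearly better.** Its exclusion restriction could fail through provider access, through the call to patients with no access by day 7, or because patients learn their arm after the visit and before the self-reported PAM. Its intervals are wider, and one binary instrument cannot answer how often or by whom. This stands: it is an option, not a required replacement.

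**Conclusion.** The point holds for the secondary access models and for the claim about provider log-ins. Access is post-randomization, self-selected and absent from Arm 2 by design. The access coefficient therefore carries D on either fitting, and a two-arm arm coefficient is also shifted by −qD. Neither can be read as the effect of use. The primary intention-to-treat comparison is not faulted.

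The direction of the argument rests on the text; its size rests on assumption. The 17% and 51% false-positive rates need D of 2 and 4 PAM points at 72% access, and nothing in the documents fixes D. The arm-coefficient shift applies only to the two-arm reading. For truly rare provider log-ins the matter is mainly pre-specification, at 0.2 to 0.4 PAM points for 5-10% excluded and an assumed 4-point difference. Section 6.0 mentions an approved Data Analysis Plan that was not supplied and may settle some of this.

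**What to change.** 1. **Section 5.1, Aim 1.** Delete the adjust-or-exclude sentence. Treat provider access as part of the Arm 1 program and report it descriptively.
2. **Section 5.1, Aim 1 and Audio recording technology.** State that access data do not enter the primary Aim 1 comparison and that no randomized patient is excluded from it, in line with Section 5.6.
3. **Section 5.6.** Fit access and listening-dose analyses within Arm 1 only. Label them exploratory and associational, not the impact of use.
4. **Optional.** If a causal effect of use is wanted, add a CACE with assignment as the instrument.
   - Report mean or risk differences, with provider-clustered standard errors and a small-sample correction, because Section 5.2 sets no number of providers.
   - For the PAM, count only access before that patient's call. Calls start at one week and may move to 10-14 days, while outreach follows day 7, so some access may come after the call.
   - State the exclusion restriction and the three ways it could fail: provider access, the outreach call, and patients learning their arm.

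Items 1 to 3 cost a few sentences and no data. They give up a causal claim that the access covariates could not support. Item 4 uses data already logged. Its price is the wider interval (PAM half-width 3.5 points at 72% access and 6.3 at an assumed 40%, against 2.5), an untestable assumption, a scale other than the planned odds ratios, and no answer on frequency or on who listened.

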5.2 Recruitment Methods

- State how many subjects will be needed.

The numbers and distribution of patient subjects is presented in Figure 3, above. As noted, a total of 1904 will be recruited from the primary care clinics and 404 from the diabetes clinics, totaling 2308, all above 18 years of age.

The primary subjects are Veterans. However, since providers will be audio recorded as well, and since we will be studying the effect of being audio recorded on the behavior and outcomes of their patients, providers will be considered as human research subjects as well. Since they are not a unit of study, there is no specific sample size.

We also plan to interview hospital leaders about the program. They are also subjects, but given the low risk to them, will likely be exempted from a formal consent process. We anticipate interviewing five leaders at each of the two facilities, for a total of 10.

- Describe when, where, how and by whom potential subjects will be identified and recruited.
- Describe materials that will be used to recruit subjects, e.g., advertisements. Include materials as an appendix or separate attachment.
- Describe any payments to subjects, including the amount, timing (at the end of the study or pro-rated for partial study participation), method (e.g., cash, check, gift card), and whether subjects will experience a delay in receiving the payment.

Recruitment will proceed as follows:

(A) Providers (physicians or nurse practitioners) will be notified of the project by the site investigator by attending their section meetings (at the invitation of the section chiefs — who have already indicated support of the project) and providing a brief description and study brochure (same as the one shared with patients). Those who wish to participate will sign a sheet providing their name and contact information. In addition, the PI will send out an email to providers who were not able to attend the meeting. The site investigator and/or RA will meet with all who indicate interest to complete the informed consent process.

NOTE: When clinical section meetings are held virtually because of the COVID-19 pandemic, these activities will also be conducted virtually. Handouts and sign-up sheets will be emailed.

Recruitment of providers for focus group participation will occur via email invitation, and is optional for all participating providers. Providers are first informed of the focus groups in during the informed consent process for the study, as detailed in the consent document. They are informed that they will be contacted about participation, that participation will be voluntary, that the focus groups will be audio recorded, and that to minimize risk, they will be asked not to use their names or the names of any patients during the focus groups. They are also informed that lunch

will be served. The email text is provided with this protocol and informs providers that "if you are interested, please reply to this message."

(B) Recruitment of patients will occur in primary care and diabetes clinics in Chicago (Jesse Brown) and Cleveland (Louis Stokes). Since the former is nearly three times larger than the latter, it is anticipated that recruitment will be proportional. However, it will continue at both site until target numbers are achieved. The method of recruitment is as follows:

In primary care, the research team will obtain the panel lists of all participating providers. These are accessed through CPRS under each providers schedule. They will then randomly select the subset of patients necessary to contact via mail 2-4 weeks prior to their scheduled appointments informing them of the study and explaining how to opt out. Based on a 2014-16 study we conducted involving audio recording visits (SDR 12-280) we plan to mail 2767 prospective subjects, taking into account that 20% opt out, decline during the outreach call, are not reachable, don't show up in clinic, or opt out on site. About a week prior to the visit the RA will then phone those who do not opt out, to achieve recruitment of 1904 patients to be distributed across 2 sites (Chicago and Cleveland) and divided by randomization, utilizing the computer-generated sequences detailed in the research to allocate 827, 827, and 250 subjects to Arms 1, 2, and 3 respectively. Those who are reached and affirm will agree to arrive approximately 20 minutes early for their appointment.

For the diabetes clinic patients, an additional 404 patients will be randomly assigned to Arms 1 and 2. The same opt out strategy described above for primary care will be employed to recruit patients to these clinics as well.

(C) Upon arrival, they will complete the informed consent process and the brief literacy screen (REALM-SF), receive the audio recording device, and instructions based on the arm of the study to which they are randomized, as to whether to keep the audio recording out in the open (Arms 1 and 2), or to conceal it (Arm 3). A code, assigned to the encounter, will be utilized as the ID on the literacy screen, and linked to the patient name and medical record number stored in the cross walk file on a separate VHA approved server. After the encounter, patient and provider participants will receive a link to access the audio if they were in Arm 1. If they are called prior to completing the process, their appointment takes precedence and they will not participate.

(D) In addition to pre-visit outreach, the RA will recruit patients at an information desk on site when they arrive in the waiting area with a poster and a brochure inviting Veterans to learn more if they are interested.* This will occur until recruitment targets are met. Those who are seeing a participating provider and want to participate will complete the informed consent process and the brief literacy screen (REALM-SF). They will receive a \$20 gift card to remunerate them for the additional work of completing the survey after the visit and for randomly participating in a follow up call for the PAM survey. If the Veteran is called prior to completing the process, their appointment takes precedence and they will not participate.

***COVID-19 MODIFICATION: As long as infection transmission remains a risk the following protocol modification will be in place:**

- Only phone based recruitment will occur.
- The informed consent process will be completed over the phone prior to the visit, except for the final signing process.
- The RA will still meet the patient in the waiting area, both masked. However, it will be a very brief meeting and they will remain 6 feet apart. There will be a small fold

up table in the waiting area. The patient will sign the consent form, collecting the audio recorder, and complete the 7 item REALM-SF which consists of reading out loud 7 words, and takes less than 1 minute.

- Post visit, the patient will return the audio recorder to the table and collect \$20 gift card from the research assistant. Again, the RA will maintain a physical distance of at least 6 feet and will remain masked.

